Statistical Plan, Results and Conclusions for:

A Clinical Decision Support Tool for Electronic Health Records (Official Title)

NCT number 02697643

Document Date: August 9, 2018

Analytic Approach.

Primary Analytic Approach. We are interested in learning whether participants in the intervention condition, BH-CDS, as compared to the control condition, treatment as usual, have (1) greater access to wraparound services, (2) more treatment visits, and (3) longer retention in treatment. As secondary hypotheses, we will examine whether the intervention condition, as compared to the control condition, will be associated with significantly (1) greater psychosocial outcomes, and (2) reduced drug use. A mixed model analytic approach was chosen for its ability to: adjust for individual-level covariates; take into account nesting of clients within counselors; and efficiently maximize the correlated nature of the repeated measures data in the design. Each mixed model will include fixed effects (condition, time and condition-by-time); random effects (clients nested within counselors); repeated measures variation (time); as well as potential counselor-level demographic covariates (e.g., experience level) and client-level demographic covariates (i.e., age). Non-significant covariates will be removed systematically. After arriving at the final model for each analysis, the condition-by-time effect will be examined for significance. In the presence of a significant condition-by-time effect, Bonferroni corrected post-hoc contrasts will be conducted to test for differences between conditions on mean change from baseline to one month follow-up and baseline to three month follow up

Analyses by Hypothesis

Primary Hypothesis 1: Clients in the experimental condition will have significantly greater matched evidenced-based and wraparound services than clients in the control condition. To address this hypothesis, a chart review was conducted to enumerate services received during the study period. The percentage of services that clients in the experimental condition received from the list of tailored recommendations was calculated. We then compared this percentage to the percentage of services that clients in the control condition would have received had they been in the experimental condition and received tailored recommendations. Because all clients participating in the study completed the PDE, we were able to determine which set of recommendations clients in the control condition would had received had they been in the experimental.

Primary Hypothesis 2: Clients in the experimental condition will have greater engagement in treatment than clients in the control condition. Engagement in treatment was calculated by dividing the number of treatment sessions attended during the study period by the total number of scheduled treatment sessions (i.e., opportunities for treatment), a sum of treatment sessions attended plus the number of scheduled sessions that the client did not show up for (no-show). An independent samples T-test was utilized to determine whether there were statistically significant differences between participants in the experimental and control groups with respect to treatment engagement.

Primary Hypothesis 3: Clients in the experimental condition will have less frequent use of substances than clients in the control condition. Use of substances was measured by the number of relapses during the study period. An independent samples *T*-test was conducted to evaluate whether participants number of relapses differed significantly between the experimental and control groups.

Primary Hypothesis 4: Clients in the experimental condition will have greater biopsychosocial functioning than clients in the control condition. Biopsychosocial functioning was captured by the seven ASI-MV composite scores. The ASI-MV was administered at baseline, 1-month follow-up and 3-month follow-up. Change in the ASI-MV composite scores was evaluated over time and across participant groups with a repeated measures mixed model.

Primary Hypothesis 5: Clients in the experimental condition will have greater cost effectiveness than clients in the control condition. Costs of services provided to the participating clients in the experimental and control conditions during the study time period was estimated in the following way. Services received by each client as documented during the chart review process for Hypothesis 1 above. The cost of each service was estimated using the CPT code for that service (e.g., group psychotherapy = 90853). To establish consistent costs, estimates of cost for each CPT code were derived from Medicare reimbursement estimates in Massachusetts using online tools (e.g., https://www.findacode.com). While not precise, use of Medicare reimbursement is often used to get a general and relative sense of service costs across states. This is especially useful for comparing groups (e.g., experimental versus control), rather than attempting to generate precise cost estimates. Costs per individual were summed and averaged for t-test comparison between experimental and control groups. If patient outcomes are superior for one group, this test would determine whether the outcome difference is associated with greater or lesser costs.

Primary Hypothesis 6: Counselors in the experimental condition will report satisfaction with the BH-CDS Program. At the end of the study, participating counselors were asked to complete a satisfaction survey, which included both open-ended questions and Likert-type rating scale questions. Due to the small number of counselors in the experimental and control groups, formal statistical significance testing was not conducted. Instead, these data were analyzed descriptively. Open-ended text were subject to qualitative thematic analysis.

Results

Counselor Participants. A total of 24 counselors at four outpatient substance abuse treatment facilities around the United States participated in the current study.

Client Participants. One hundred and ninety patients completed consent forms and completed baseline surveys. Of these, 140 participants were fully enrolled into the study (completed the PDE, counselors obtained recommendations from the BHCDS system, participants completed the baseline survey). Forty-seven participants were randomized into the control, TAU, condition and 93 were randomized into the experimental condition. Demographics were relatively similar across the experimental and control conditions.

Primary Hypothesis 1: Clients in the experimental condition will have significantly greater matched evidenced-based and wraparound services than clients in the control condition. Results test indicated no significant difference for experimental and control groups.

Primary Hypothesis 2: Clients in the experimental condition will have greater engagement in treatment than clients in the control condition. T-tests indicated that the experimental and control groups did not differ with respect to treatment engagement.

Primary Hypothesis 3: Clients in the experimental condition will have less frequent use of substances than clients in the control condition. The mean number of relapses during the study period for the experimental group was not significantly different from the control group.

Primary Hypothesis 4: Clients in the experimental condition will have greater biopsychosocial functioning than clients in the control condition. Results for psychiatric status, medical status, alcohol use, family status, or drug use were not significant. Employment status results suggest that participants in the experimental, CDS, condition had significantly fewer legal problems than controls.

Primary Hypothesis 5: Clients in the experimental condition will have greater cost effectiveness than clients in the control condition. The CDS program did not yield significantly different costs effectiveness than the control group.

Primary Hypothesis 6: Counselors in the experimental condition will report satisfaction with the BH-CDS Program. Overall, counselors found it easy to complete the CDS program and reported that their clients' reaction was "neutral" or "positive" (no counselors reported a negative client reaction).

Counselors exposed to the tailored recommendations, reported that they were easy to understand, easy to integrate into the client's treatment plan, and useful for informing treatment decisions and were more likely to incorporate the tailored recommendations into future treatment planning.

Conclusion

Although the use of clinical decision support is promising, the present effort was unable to empirically demonstrate a direct impact on outcome, retention, amount of service delivered or cost. Further research on the impact of clinical decision support for substance use treatment is warranted.

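### The listed random effects leave out counselor differences in client change, so the condition-by-time test for the ASI-MV scores runs above 5% if counselors were assigned to arms

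*SAP*

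**What the plan says.** Under Primary Analytic Approach, one reason given for a mixed model is that it can "take into account nesting of clients within counselors". The components are then listed. The fixed part is "Each mixed model will include fixed effects (condition, time and condition-by-time", and the random and repeated part is "random effects (clients nested within counselors); repeated measures variation (time", with covariates added. No term crosses counselor with time, and neither counselor-robust errors nor counselor-based degrees of freedom are mentioned.

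The decision rule is "After arriving at the final model for each analysis, the condition-by-time effect will be examined for significance". If that effect is significant, corrected contrasts "test for differences between conditions on mean change from baseline to one month follow-up and baseline to three month follow up".

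Under Analyses by Hypothesis, only Hypothesis 4 names a repeated measures mixed model, for seven composite scores: "The ASI-MV was administered at baseline, 1-month follow-up and 3-month follow-up". Hypotheses 2, 3 and 5 use t-tests, Hypothesis 1 names no test, and Hypothesis 6 is descriptive.

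On allocation the SAP points two ways. The Client Participants paragraph in the Results describes 47 and 93 participants as randomized. The Hypothesis 6 text declines formal testing "Due to the small number of counselors in the experimental and control groups", which places counselors in arms.

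**The concern.** A random effect that is constant over time is subtracted out of any change from baseline. The counselor term is there to deal with clustering, but the deciding test compares changes. Clustering affects that test through counselors whose clients improve more or less than others' clients do, and nothing in the listed model represents this.

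If each counselor sits in one arm, such differences add to the variance of the between-arm comparison of change. The model then reports too small a standard error, and each of the seven tests rejects too often. The Results report one significant difference, and it falls under Hypothesis 4, so the only favourable comparison between arms may rest on this error term.

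**Working it through.** **Inputs from the SAP.** 140 clients, 93 experimental and 47 control; 24 counselors; three visits. Mean clients per counselor: m = 140/24 = 5.83.

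**Assumptions, because the SAP gives no figure.** Two-sided 5% level; ICC of change 0.02 to 0.10; residual variance 0.5; counselors split 16/8 or 12/12 between arms. The SAP states no error rate or standard error for this test, so there is no figure to reproduce.

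**Step 1: cancellation.** Write the outcome of client i of counselor c at visit t as fixed part + a(c) + b(ci) + e(cit). The change from baseline is fixed part + e(cit) − e(ci0), because a(c) and b(ci) drop out. The standard error of the between-arm difference in change is therefore √[2 × 0.5 × (1/93 + 1/47)] = √0.03203 = 0.179.

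Exact generalized least squares for the 16/8 layout, with client variance 0.5, gives 0.17897 at counselor variances of 0, 0.05, 0.1, 0.3 and 0.6. Over the same range the standard error of the baseline arm difference rises from 0.179 to 0.380. The counselor term therefore acts on levels and not on change. With 20% and 35% of visits missing at 1 and 3 months, the 3-month contrast moves only from 0.21521 to 0.21577, about 0.3%.

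**Step 2: what is left out.** Add a counselor-by-time effect g(ct). The change now contains g(ct) − g(c0), shared by all clients of counselor c. The ICC of change is ρ = var(g)/[var(g) + var(e)]. With counselors in one arm each, the variance of the contrast is multiplied by DE = 1 + (m − 1)ρ = 1 + 4.83ρ.

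- One contrast: actual level = 2 × [1 − Φ(1.96/√DE)].
- Joint two-df test, large-sample form: actual level = 0.05^(1/DE).

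| ρ | DE | one contrast | joint test, formula | joint test, simulated 16/8 | joint test, simulated 12/12 |
|---|---|---|---|---|---|
| 0 | 1.00 | 5.0% | 5.0% | 4.9-5.0% | 4.9-5.1% |
| 0.02 | 1.10 | 6.1% | 6.5% | 6.2-7.0% | 6.1-6.4% |
| 0.05 | 1.24 | 7.9% | 9.0% | 8.5-9.2% | 8.2-8.3% |
| 0.10 | 1.48 | 10.8% | 13.3% | 13.0-13.5% | 12.0-12.1% |

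The simulations used the complete-data F test with 2 and 276 df under no treatment effect, with 10,000 to 20,000 runs per setting. The ranges come from repeated sets.

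**Step 3: the other allocation.** When clients are allocated irrespective of counselor, the same test rejects 5.0% to 5.7% of the time for ρ up to 0.20. The counselor's effect on change is then shared by both arms and largely balances out.

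**Step 4: with the missing term.** For the 16/8 layout the standard error of the contrast becomes 0.200 at ρ = 0.05 and 0.218 at ρ = 0.10, against 0.179 from the listed model. Testing against a counselor-level error term gave 4.7% to 5.2% in simulation.

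**The case against.** The strongest objection is that the only explicit statement about randomization concerns participants. On that reading the error rate is essentially correct and nothing needs re-running. This stands as far as it goes: the inflation is conditional. It does not dispose of the point, because the Hypothesis 6 wording puts counselors in arms and the SAP never reconciles the two.

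A reader might infer that the deciding test receives no protection at all against clustering. That goes too far. A counselor effect that is constant over time is fully dealt with by taking changes and needs no further correction. Only heterogeneity in change is left out.

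A reader might also infer that an intercept-only model was certainly fitted. The SAP does not say so; the random part names a grouping structure and may be under-described. The criticism is of the model as listed.

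Nor can one infer that the significant result is a false positive. The sentence reporting it mixes employment status with legal problems and does not say which test produced it. The ICC is also unknown: at 0.02 the excess is only one to two percentage points. Composites that were not significant under too small a standard error would not be expected to become significant under a larger one, and the SAP's overall conclusion is already negative. These arguments lower the severity. They leave the omission itself in place.

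**Conclusion.** The point holds in conditional form. The random effects listed do not enter the condition-by-time test, so the stated aim of accounting for nesting is not met for counselor differences in change. Cancellation is exact with complete data and nearly so with the missingness tried.

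The harm requires two things that the SAP does not establish: that counselors were assigned to arms, and that they differ in their clients' change. If both are true, the nominal 5% joint test has a real level of about 6%, 8-9% and 12-13% at an ICC of change of 0.02, 0.05 and 0.10. If clients were allocated irrespective of counselor, it stays near 5%. The reach is the seven ASI-MV models. The analysis should be corrected, but the point is not critical while the allocation unit is unsettled.

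**What to change.** 1. State the unit of allocation, and reconcile the Client Participants paragraph with the Hypothesis 6 text.
2. If counselors were assigned to arms, add a random counselor-by-time term to the Hypothesis 4 model and keep the client-level repeated-measures covariance. Test condition-by-time with Kenward-Roger or Satterthwaite degrees of freedom. Re-run the seven composites and report the one significant result from that model, naming the composite and the test.
3. If counselors treated clients in both arms, the listed model is about adequate for type I error. The counselor-by-time term is then optional, and the degrees of freedom should not be tied to the 24 counselors.

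The cost is a change of wording and, in the second case, a re-run on existing data with somewhat larger standard errors: about 12% larger at an ICC of change of 0.05 (0.200/0.179) and 22% at 0.10 (0.218/0.179), under the 16/8 split. The simulated return to 5% used a counselor-level error term. The full model in item 2, with about six clients per counselor, was not simulated, so its convergence and degrees of freedom should be checked when it is fitted.

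### The ASI-MV mixed models choose their covariates by significance from an open list; fix a short set in advance (minor: the planned condition-by-time test is little affected)

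*SAP*

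**What the plan says.** Under Primary Analytic Approach, each mixed model has fixed effects for condition, time and their interaction, "random effects (clients nested within counselors"), repeated measures over time, and "potential counselor-level demographic covariates (e.g., experience level) and client-level demographic covariates (i.e., age"). The next step is "Non-significant covariates will be removed systematically". Testing comes only after that: "After arriving at the final model for each analysis, the condition-by-time effect will be examined for significance". A significant interaction leads to Bonferroni-corrected contrasts on change from baseline to one and to three months.

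Under Analyses by Hypothesis, only Hypothesis 4 is described as using a mixed model, for the seven ASI-MV composites at baseline, one month and three months. Hypotheses 2, 3 and 5 use t-tests with no covariates, Hypothesis 1 names no model, and Hypothesis 6 is descriptive.

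The Results give the sizes: "A total of 24 counselors at four outpatient substance abuse treatment facilities", and "140 participants were fully enrolled into the study".

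**The concern.** This is a stated method, not a detail left to another document. In a randomised comparison, covariates are adjusted for because they are expected, beforehand, to predict the outcome. Whether they reach significance in the sample at hand is not a sound criterion. The rule here has three weaknesses.

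- The counselor candidates are only possibilities, illustrated by one example, so the starting model is not fixed.
- No p-value threshold, removal order or stopping rule is given, so two analysts could reach different final models.
- Selection is repeated for each analysis, so the seven composites may end with seven different adjustment sets.

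Counselor covariates are also judged on only 24 units, so useful ones will often be discarded. What is at stake is mainly reproducibility. The one significant between-arm result that the document reports comes from Hypothesis 4, and the document does not say which covariates remained in that model.

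**Working it through.** The SAP gives no power, alpha, intraclass correlation (ICC) or standard deviation, so there is no planned figure to reproduce. The checks use the 24 counselors and 140 clients (140/24 = 5.8 per counselor) and, where needed, the 93:47 allocation. Everything else below is an assumption.

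**1. How often is a useful counselor covariate kept?** Assume a two-sided 0.05 threshold and counselor effects observed without error. For true correlation r and J = 24, the test has J − 2 = 22 degrees of freedom, critical value 2.074 and noncentrality

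λ = √J · r / √(1 − r²).

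At r = 0.3, λ = 4.899 × 0.3 / √0.91 = 1.54. At r = 0.4, λ = 4.899 × 0.4 / √0.84 = 2.14.

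| r | 0.2 | 0.3 | 0.4 | 0.5 | 0.6 |
|---|---|---|---|---|---|
| Chance kept | 16% | 31% | 53% | 77% | 94% |

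Treating the covariate as random rather than fixed gives 30% at 0.3 and 51% at 0.4.

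**2. The same question inside a mixed model.** A simulation under no treatment effect (1,500 runs per scenario) used a REML random-intercept model with three counselor covariates, one of them real, plus age, and backward elimination at 0.05. ICC was 0.05 or 0.15, and the real covariate's correlation with the counselor effect was 0.4 or 0.7. The real covariate was kept in 14-72% of runs.

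**3. Effect on a between-condition main effect in that simulation.** Monte Carlo error is about 0.6 points.

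| Allocation assumed | SE / true SD, all kept | SE / true SD, selected | Type I error, all kept | Type I error, selected |
|---|---|---|---|---|
| By counselor | 0.98-1.05 | 0.93-1.00 | 3.7-5.9% | 4.7-6.3% |
| By client | 0.98-1.02 | 0.97-1.01 | 4.6-5.4% | 5.1-5.7% |

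This is not the effect that the SAP tests.

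**4. Effect on condition-by-time, complete data.** Age and counselor experience are constant across a client's visits and enter as main effects only, so they cancel from within-client change. In three simulated complete three-visit data sets, the interaction estimates and standard errors agreed to five decimals with and without the covariates.

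**5. Effect on condition-by-time, missing follow-up.** Two simulations used assumed variance components.

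- With 40% of follow-up visits missing at random (600 runs per scenario), type I error was 7.8% with all covariates kept and 7.7% after selection under allocation by counselor, and 4.3% for both under allocation by client. The excess over 5% in the first pair is common to both models, so selection does not cause it. Decisions differed in at most 0.3% of runs.
- With missingness that depended on the covariates (150 runs per scenario), selection moved single-trial estimates by up to about a quarter of a standard error and changed about 1% of decisions.

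**The case against.** The strongest reply is that the rule does almost nothing to the planned test. The counselor random effect stays in every model, so variance explained by a dropped counselor covariate moves into the between-counselor component and is still counted. The tested effect is condition-by-time, where covariate main effects cancel on complete data. Both points stand, and they are why this is minor.

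Three stronger readings are tempting, and the documents do not support them.

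- **A reader might infer that standard errors are clearly too small, with type I error of 7.7-9.1%.** Such figures arise from ordinary regression on 24 counselor means, split 8 against 16, with four to six candidate covariates and a test of the arm main effect. The SAP plans a different model and tests a different effect. It names two covariates and gives no 8:16 split. It says that participants were randomized, although it also mentions counselors in the two groups.
- **A reader might infer a larger effect on engagement, relapses or cost.** The general approach does present the mixed model as primary for services, visits and retention. The hypothesis sections, however, describe covariate-free t-tests for engagement, relapses and cost, so nothing is removed there.
- **A reader might infer that the one significant Hypothesis 4 result is a product of selection.** The document does not list the covariates kept or dropped, so this can be neither shown nor excluded.

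What survives the reply is that the adjustment set is data-dependent and undocumented, and that avoiding this costs very little.

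**Conclusion.** The point holds as a minor specification fault. The Hypothesis 4 models take their covariates from the outcome data, from an open list and by an incomplete rule. With 24 counselors, a counselor covariate correlated 0.3 to 0.4 with the outcome would be dropped in roughly half to 70% of trials. The consequence for the condition-by-time test is nil with complete data and small with missing follow-up. These sizes rest on an assumed 0.05 removal threshold and on assumed covariate strengths, variance components and missingness patterns, none of which the SAP gives. The 150-run check is too small to give more than an order of magnitude.

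**What to change.** Delete the removal sentence. Name a short closed set, for example client age and counselor experience, which the SAP already mentions. Keep it in all seven ASI-MV models whatever its significance, and show the unadjusted model as a sensitivity analysis. Do not add the baseline score as a covariate, because baseline is already one of the repeated outcomes in this model.

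Results already exist, so the report should also state which covariates each Hypothesis 4 model kept and dropped. A refit with the fixed set should be labelled as done after the data were seen.

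The cost is a few lines of wording, one refit per composite, and one or two degrees of freedom that may go to weak covariates.

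### After a significant condition-by-time test, Bonferroni on the two change contrasts is stricter than 5% control of that pair requires: lost efficiency, not invalidity

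*SAP*

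**What the plan says.** The SAP, under Primary Analytic Approach, sets a two-step procedure for each mixed model. First: "After arriving at the final model for each analysis, the condition-by-time effect will be examined for significance". Second: "In the presence of a significant condition-by-time effect, Bonferroni corrected post-hoc contrasts will be conducted to test for differences between conditions", the contrasts being on "mean change from baseline to one month follow-up and baseline to three month follow up". There are thus two contrasts per outcome, run only if the first test is significant.

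Under Primary Hypothesis 4 the SAP gives the visits: "The ASI-MV was administered at baseline, 1-month follow-up and 3-month follow-up". This is the only hypothesis section that describes a repeated measures mixed model, and it covers seven composite scores. The arm sizes are in the Results: "Forty-seven participants were randomized into the control, TAU, condition and 93 were randomized into the experimental condition".

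The SAP states no significance level. It gives no reason for adding Bonferroni after the first test, and does not say that the correction covers anything beyond these contrasts.

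**The concern.** The two contrasts are guarded twice, once by the condition-by-time test and once by Bonferroni. If the first guard alone holds the pair's familywise error at 5%, the second only pushes the error below the intended level and takes power from the contrasts. The contrasts are there to show at which visit the arms diverge, and whether a difference at one month persists at three. With 47 controls there is little power to give away on that question.

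**Working it through.** **Inputs from the SAP.** Two arms (47 and 93 clients), three visits, two change contrasts, a condition-by-time gate. There is no alpha, power or effect size for this point, so there is no SAP figure to reproduce.

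**Assumptions.** Alpha 0.05 two-sided for gate and contrasts; time categorical; all 140 clients complete; equal SD at each visit; between-visit correlation 0.6; no counselor effect. Effects are in SD of the outcome at a visit.

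**Step 1: logic.** Let δ1 and δ3 be the arm differences in change to one and three months. The interaction has (2 − 1) × (3 − 1) = 2 degrees of freedom, and its null is δ1 = δ3 = 0. That is the only intersection of the two contrast nulls. Test each contrast at α only after the gate rejects at α:

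- Both nulls true: a false claim needs the gate to reject, so its probability is at most α.
- One null true: a false claim needs that contrast's own test to reject, so again at most α.
- Neither null true: no false claim is possible.

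The pair's error is therefore at most 0.05 in every case. The SAP's extra step tests each contrast at 0.05/2 = 0.025.

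**Step 2: error by simulation.** SD of change = √(2 × (1 − 0.6)) = 0.894. Correlation of the two changes = 0.4/0.8 = 0.5. Standard error of a contrast = 0.894 × √(1/47 + 1/93) = 0.160. The gate is F on 2 and 137 df; the contrasts are t on 138 df.

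| Truth | As planned | Contrasts at gate level |
|---|---|---|
| No effect at either visit: any false contrast | 3.6% | 4.2% |
| 1.0 SD at one visit only: false claim at the other | 2.5% | 5.0% |

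**Step 3: power.**

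| Effect (1 month, 3 months) | Measure | As planned | Contrasts at gate level | Gain (points) |
|---|---|---|---|---|
| 0.5, 0.5 | each contrast | 79.6% | 84.5% | 4.9 |
| 0.5, 0.5 | both contrasts | 69.3% | 78.7% | 9.4 |
| 0.4, 0.4 | each contrast | 57.4% | 63.5% | 6.1 |
| 0.4, 0.4 | both contrasts | 43.0% | 54.6% | 11.6 |
| 0.25, 0.5 | 1-month contrast | 24.2% | 33.2% | 9.0 |
| 0.25, 0.5 | 3-month contrast | 77.2% | 78.7% | 1.5 |

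With equal effects, power for at least one contrast changes by under 1 point.

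**Step 4: sensitivity.** A second calculation used normal approximations, effects in SD of change, and correlation 0.5 between the changes. At 0.5 SD, planned against gate level: 69.7% against 75.4% per contrast, 56.8% against 67.8% for both, and 82.6% against 83.1% for at least one. With no effect at either visit, error at gate level was 4.6%, 4.2% and 3.5% for correlations of 0.2, 0.5 and 0.8. With a 1-df linear-trend gate, error also stayed at or below 5% within simulation error.

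**Step 5: seven composites.** Suppose seven independent composites (assumed), with gates at 0.05/7 but contrasts at 0.05. If one, three or all seven have a large effect at one visit only, familywise error is about 9%, 17% and 30%. The last follows directly: 1 − 0.95⁷ = 30.2%. With contrasts at 0.025 it is about 6%, 10% and 16%. With gate and contrasts both at 0.05/7, each composite contributes at most 0.05/7 by Step 1, so the total is at most 7 × 0.05/7 = 0.05.

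**The case against.** The strongest reply is that the plan is valid and conservative, so a sharper valid procedure is only a preference. The first half stands: no type I error is inflated and nothing is contradictory. The second half is weaker, because the change gains power while keeping 5% control of the pair.

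A second reply is that Bonferroni does protect. A reader might infer that the step buys nothing; the figures do not support that. It halves the error from 5.0% to 2.5% when one contrast is null, which is more than 5% control of the pair requires. It also limits error across composites if only the gates are corrected (about 16% instead of 30% in the worst case of Step 5). Neither version controls error across composites there, so the remedy must carry any composite-level correction into the contrasts.

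A reader might also infer that a significant interaction with no significant contrast is uninterpretable and that the change removes it. It occurs in about 1.5% of trials or fewer in these scenarios, and the change does not abolish it: 0.4% remains in the 0.25/0.5 case. It also has a meaning: trajectories differ, but the visit is not identified.

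Finally, the document already contains results. It does not say which test each reported composite result refers to, so one cannot conclude that a finding was lost.

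**Conclusion.** The point holds as a free improvement. Within one outcome, the condition-by-time test already secures 5% familywise control for the two contrasts, and Bonferroni on top is stricter than that requires. At 0.4 to 0.5 SD at both visits the cost is about 5 to 6 points of power per contrast and 9 to 12 points for showing both. The loss falls on locating the difference in time, not on finding one.

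The closed-testing argument needs gate and contrasts to be valid tests at the same level. The power figures rest on the assumed alpha, effects, correlation and complete data, and ignore counselor nesting and covariate selection. The reach is the Hypothesis 4 mixed models. Nothing here shows that multiplicity is controlled across the seven composites or the six primary hypotheses: the SAP states no such correction, and the Bonferroni step as written does not supply one.

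**What to change.** Replace the Bonferroni sentence with:

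> If the condition-by-time test is significant, the 1-month and 3-month contrasts are each tested at the same significance level as that condition-by-time test (closed testing).

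State that level. If a correction across the seven ASI-MV composites is used, for example 0.05/7 per composite, it should set the level of both the gate and its contrasts. Correcting the gate alone and testing contrasts at 0.05 does not control error across composites.

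The cost is one sentence and no new data. Since results are already reported, any contrasts re-tested at the new level should be labelled a re-analysis and shown beside the Bonferroni-corrected ones.
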